
Objective(s):
	
 - External validation of pre-existing prognostic scores of traumatic haemorrhages at different times of care (Scene of Injury, admission at the trauma room) in order to assess their overall performance, discrimination and calibration in the prediction of massive transfusion and haemorrhagic death. - Comparison of score performances (Overall performance, discrimination and calibration).

Outcome(s):
	
Primary study outcome :
 
 - Massive transfusion defined by a transfusion equal to or greater than 10 Red blood cell (RBC) / 24 hours or ≥ 3 RBC in the first hour if available in the Swiss Trauma Registry. 
Secondary study outcome :
 
 - Death due to bleeding (if available in the registry) - Early death (< 24 hours) - Coagulopathy at admission defined by INR > 1.2, quick TP < 70% or Fibrinogen < 1.5 g/L (6,7,8)

Study design:
	
Observational non-interventional study based on a multicentric anonymized registry

Inclusion / Exclusion criteria:	
Study population: All adult trauma patients treated at twelve Swiss trauma centres Level I from 01.01.2015 to 31.12.2019 with eligible criteria of the Swiss Trauma Registry (STR) are included. All data from the register are anonymised without any access to medical files. The identity of the trauma patients, date of birth, address and trauma scene location are unknown (as mandatory by the swiss law: Art. 2 ORH).
 
Inclusion criteria:
 
- Age > 16 years old- ISS (Injury Severity Score) ≥ 16 and/or AIS head (Abbreviated Injured scale) ≥ 3 
Exclusion criteria:
 
- Age < 16 years old- ISS < 16 and or AIS < 3- Isolated Burns (including electric shock) or if the burn is clearly the primary injury- Patients arriving at the trauma room with no sign of life and no diagnostic/therapeutic measures have been initiated for them- Choking or hanging patient without any other injury.- Drowning patients
--	---

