4.2.2. Exclusion criteria

- Age < 16 years old
- ISS < 16 and/or AIS head < 3
- Isolated Burns (including electric shock) or if the burn is clearly the primary injury
- Patients arriving at the trauma room without signs of life and no diagnostic/therapeutic measures have been initiated for them
- Choking or Hanging patient without any other injury
- Drowning patients

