5.2.4. Calibration

Calibration is the agreement between observed and predicted outcomes. The investigators will mostly estimate calibration as the difference between the mean predicted and observed probabilities and the ratio of the predicted and observed number of events (P/O). The investigators will plot the observed and predicted probabilities of massive transfusion by decile of the score and with local regression based on LOESS algorithm. The investigators will estimate the calibration intercept and slope of the calibration plot as a measure of spread between predicted and observed outcome. Ideally, the intercept would be zero indicating that the predictions are neither systematically too low or too high and the slope would be 1.

Unfortunately, the investigators cannot estimate the calibration of the BATT score, because of its different outcome (death due to bleeding and not the massive transfusion as the TASH and ABC score). For the BATT, calibration will be assessed with the outcome of death due to bleeding or early death.

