5.2.1. Imputation method

To estimate baseline risk for the full dataset, the investigators will replace missing predictors using multiple imputation by chained equations on sex, age, systolic blood pressure, respiratory rate, heart rate, Glasgow coma scale, Haemoglobin, base excess, type of injury (penetrating/blunt) Instable pelvis fracture and open/dislocated femur fracture with 20 imputed dataset. All analysis and results will be present in two subgroups: missing data imputed and missing data excluded.

5.2.2. Early deaths and early deaths with haemorrhage as a proxy for death due to bleeding

Because the investigators don't know if the Swiss Trauma Registry record the cause of death, the investigators expect some missing data about death due to bleeding as a secondary outcome. In case of missing data on secondary outcomes, the investigators will use early deaths and early deaths with evidence of haemorrhage as a proxy for death due to bleeding. Specifically, the investigators will included deaths from all causes within 12 hours of injury (excluding massive destruction of skull or brain; asphyxia, drowning and hanging are already excluded from the STR) and deaths between 12 to 24 hours with evidence of bleeding (Activation of massive transfusion protocol or blood within 6 hours or an abbreviated injury scale (AIS) diagnosis associated with haemorrhage: Blood loss >20%, Aorta [OR] Vena Cava [OR]carotid [OR]femoral [OR]Major arteries [OR]veins AND laceration, - Spleen [OR]liver [OR] Kidney [OR] Myocardium [AND] major laceration, major haemothorax, retroperitoneum haemorrhage).

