5.3 Subgroup analyses

If the sample size permits, the investigators will conduct subgroup analysis in different subpopulations for the primary and secondary outcomes. The investigators will create the following subgroups in our MTP study:

- Subgroup 1: subdivide the population into two groups: with or without isolated severe traumatic brain Injury (TBI) with AIS HEAD ≥ 3 and AIS thorax/abdominal <3 and/or AIS lower extremity < 4 .
- Subgroup 2: subdivide the population into two groups: with or without anticoagulation treatment before trauma.

- Subgroup 3: subdivide the population into two groups: with or without trauma-induced coagulopathy.
- Subgroup 4: subdivide the dataset in prehospital settings and in-hospital settings.
- Subgroup 5: All analysis and results will be present into two subgroups: missing data imputed and missing data excluded with the complete case analysis.
- Subgroup 6: The investigators will test the heterogeneity of the performance parameters of each centre and the investigators will potentially exclude data from centre with homogeneous case mixes.
- Subgroup 7: subdivide the population into two groups: low-volume prehospital fluid replacement (<1500 ml) and High-volume prehospital fluid replacement (>1500ml).

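### If cause of death is not recorded, the bleeding-death proxy counts non-bleeding head-injury deaths before 12 hours, so BATT would appear to under-predict

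*SAP*

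**What the plan says.** The proxy is a fallback. SAP 5.2.2 (Early deaths and early deaths with haemorrhage, under Missing Data) gives the reason: "Because the investigators don't know if the Swiss Trauma Registry record the cause of death". It then sets the rule: "In case of missing data on secondary outcomes, the investigators will use early deaths and early deaths with evidence of haemorrhage as a proxy".

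The proxy has two parts:

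- **Before 12 hours:** "deaths from all causes within 12 hours of injury (excluding massive destruction of skull or brain". The text adds that asphyxia, drowning and hanging are already outside the registry. No evidence of bleeding is required, and the skull or brain exclusion carries no AIS code or severity level.
- **12 to 24 hours:** "deaths between 12 to 24 hours with evidence of bleeding", meaning activation of a massive transfusion protocol, blood within 6 hours, or one of a list of haemorrhagic AIS diagnoses.

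The cohort enters on "ISS (Injury Severity Score) ≥ 16 and/or AIS head (Abbreviated Injured scale) ≥ 3" (Protocol synopsis; SAP 4.2.1 agrees).

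The outcome matters most in SAP 5.2.4: "For the BATT, calibration will be assessed with the outcome of death due to bleeding or early death". SAP 5.2.1.1 extends all the primary-outcome analyses to the secondary outcomes. SAP 5.3, Subgroup 1, splits the population "with or without isolated severe traumatic brain Injury (TBI"), and all subgroup analyses depend on sample size.

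**The concern.** The exclusions listed for deaths before 12 hours show that the authors wanted non-bleeding deaths out of the proxy. The rule removes only the most extreme head injuries. Other fatal traumatic brain injury (TBI) before 12 hours stays in, although the cohort admits patients on head injury alone.

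The fallback may well be used. Table 1 of the SAP requests date and time of death and the early-death indicators, but not cause of death. The outcome variables in the Protocol synopsis do not list it either, although the synopsis allows complementary variables to be requested.

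At stake is the bleeding-specific calibration of BATT. SAP 5.2.4 rules out calibrating BATT on massive transfusion, and early death is an all-cause outcome. Without cause of death, this proxy is therefore the only target that claims to measure bleeding. The score comparison on death due to bleeding would use the same events. SAP 4.4 discusses misclassification of massive transfusion, but the SAP does not discuss misclassification of this proxy.

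**Working it through.** **Step 1. Apply the rule to three records.**

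| Record | Evidence of bleeding | Death at | Proxy |
|---|---|---|---|
| Isolated brain injury, AIS head 5, not massive destruction | none | 8 h | counted |
| Same patient | none | 13 h | not counted |
| Major liver laceration, blood at 1 h | yes | 8 h | counted |

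The first two records differ only in the time of death.

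**Step 2. Check that such patients are in the cohort.** Under the inclusion rule AIS head ≥ 3 is sufficient, though not the only route. The SAP 4.2.2 exclusion, "ISS < 16 and/or AIS head < 3", is loosely worded. Read literally with 'or', it would leave only patients with AIS head ≥ 3. On neither reading is isolated head injury removed as a class.

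**Step 3. Direction of the bias.** Let B be the true bleeding deaths and F the non-bleeding deaths that the proxy adds. For a score calibrated to bleeding death, the predicted number is B and the observed number is B + F:

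P/O = B / (B + F), which is below 1 whenever F > 0.

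**Step 4. Illustrative size.** The plan has no figure to reproduce. Only the projected N = 10,000 comes from the documents (SAP 3.2); every rate below is an assumption.

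F = 10,000 × share with isolated severe TBI × share of these dying before 12 h without bleeding × share not removed as massive destruction (taken as 0.75)

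- Low: 10,000 × 0.30 × 0.01 × 0.75 = 22.5
- Middle: 10,000 × 0.40 × 0.02 × 0.75 = 60
- High: 10,000 × 0.50 × 0.04 × 0.75 = 150

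P/O by assumed number of true bleeding deaths (1%, 2%, 3% and 5% of 10,000):

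| F | B = 100 | B = 200 | B = 300 | B = 500 |
|---|---|---|---|---|
| 22.5 | 0.82 | 0.90 | 0.93 | 0.96 |
| 60 | 0.625 | 0.77 | 0.83 | 0.89 |
| 150 | 0.40 | 0.57 | 0.67 | 0.77 |

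For the middle row: 100/160 = 0.625, 200/260 = 0.77, 300/360 = 0.83, 500/560 = 0.89. On the absolute scale, mean predicted minus mean observed is −60/10,000 = −0.6 percentage points.

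**Step 5. Discrimination.** With f = F/(B + F) and the same non-events, the proxy C-statistic is (1 − f) × C for bleeding deaths + f × C for the added deaths. Its direction depends on how each score ranks the added deaths, which the documents do not show.

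**The case against.** - **Reach.** The proxy is a fallback for one secondary outcome, and massive transfusion, the primary outcome, does not use it. This stands. A reader might infer that the main comparison of scores is compromised; the documents do not support that.
- **Mitigation.** Subgroup 1 covers secondary outcomes, and its stratum without isolated TBI would remove many of the misclassified deaths. Table 2 also reports deaths before 12 hours and at 12 to 24 hours separately. This helps in part. However, the subgroup depends on sample size, its definition contains an ambiguous 'and/or', and the outcome in the whole cohort stays as written.
- **Size.** The share removed as massive destruction is arbitrary because the term is undefined; a broader coding would shrink F. More true bleeding deaths would also bring P/O closer to 1. This stands, so no cell of the table is an estimate.
- **A reason for the broad rule.** SAP 4.4 notes that some patients die before they can receive enough blood to qualify as massively transfused. Requiring transfusion evidence in very early deaths could lose true bleeding deaths and build transfusion into the outcome, possibly favouring TASH and ABC. This is a fair argument against replacing the broad proxy. It is weaker against adding a strict one, because the listed AIS diagnoses count as evidence without any transfusion.
- **Glasgow Coma Scale.** The scale is in the imputation list but is an item of neither TASH nor ABC. A reader might infer that BATT contains it and would gain a spurious discrimination advantage from brain deaths. BATT's items appear nowhere in the documents, so this cannot be concluded.

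**Conclusion.** The concern holds, conditional on cause of death being unavailable. The proxy then classifies the same non-bleeding head-injury death by the clock, and this error can only lower P/O for a score calibrated to bleeding death. True bleeding deaths missed elsewhere in the rule would push P/O the other way, but nothing in the plan suggests that the two errors cancel.

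The size cannot be derived from the documents. Sixty false events would give a P/O of about 0.62 to 0.77 with 100 to 200 true bleeding deaths, and 0.83 to 0.89 with 300 to 500. Over all the assumptions shown, P/O runs from 0.40 to 0.96. What is established is the misclassification and the direction of the bias it produces, not its magnitude.

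**What to change.** In SAP 5.2.2, before the data are received:

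1. Define the skull or brain exclusion by AIS codes.
2. Keep the current proxy and prespecify a second, strict one. In the strict version a death within 12 hours with AIS head ≥ 3 counts only if it meets the evidence rule already written for 12 to 24 hours: a listed haemorrhage AIS code or blood within 6 hours. Massive transfusion protocol activation can be used only if that field is obtained, because Table 1 does not list it.
3. Report BATT calibration (P/O, intercept, slope) and the comparison of scores under both proxies, with the number of deaths that change class.
4. State that the bleeding-specific calibration conclusion will not rest on the broad proxy alone.

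The cost is a wording change, one derived variable and one repeated analysis. AIS codes and timed red-cell units are already requested in Table 1. The strict version may miss some very early bleeding deaths without recorded evidence, and it still counts a head-injury death in a patient who received blood but did not die of bleeding. That is why both versions should be reported.

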4.2 Eligibility

All trauma patients included in the STR between 01.01.2015 and 31.12.2019 have been recorded according to these inclusion criteria of the STR⁶:

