4.2.1. Inclusion criteria

- Age > 16 years old
- ISS \geq 16 and/or AIS head \geq 3

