Vitamin K (doses, date/time)		X	
rFVIIa		X	
Fibrinogen (doses, date/time)		X	
Platelets units (number, date/time)		X	
Red Blood Cell (number, date/time)		X	
prothrombin complex concentrate		X	
Fresh frozen plasma (number, date/time)		X	
Imaging			
Type of Imaging		X	
CT or FAST positive for free fluid		X	
Outcome			
Date and time of death			X
Early death (<12 hours)	X	X	X
Early death (< 24h)			X
Massive Transfusion (defined by 10 RBC/24h)			X
Diagnosis			
Code AIS		X	
Final ISS		X	
Scores			
TASH Score	X	X	
ABC Score	X	X	
BATT Score	X	X	

Table 2. Summarize of potential baseline characteristics.

Age, mean (SD)
 
 - ≥ 65 years old, N (%) - < 65 years old, N (%) 
Sex male, N (%)
 
Mechanism of Injury: N (%)
 
 - Penetrating - Blunt 
Circumstances, N (%)
 
 - Road traffic Injury 
 ➤ Car ➤ Motorcycle ➤ Bicycle ➤ Pedestrian ➤ Other (train, boat) - Fall 
 ➤ > 3 meters ➤ < 3 meters ➤ Unclear - Gunshot - Stabbing - Explosion - Avalanche - Other - Unknown 
Physician staffed ambulance, N (%)
	
Prehospital SBP, mean (SD)
 
 - SBP < 90 mmHg, N (%) - SBP >90 mmHg, N, (%) 
Prehospital HR, mean (SD)
 
 - HR > 120/min, N (%) - HR < 120/min, N (%) 
Prehospital GCS, N (%)
 
 - 3-8 - 9-12 - 13-15 
Prehospital CPR, N (%)
 
ISS mean (SD)
 
ISS by categories, N (%)
 
 - 9-15 - 16-24 - 25-34 - ≥ 35 
Overall AIS score ≥3, N (%)
 
Severe head injury (AIS head ≥3), N (%)
	
ABC score, mean (SD)
 
0-1, N (%)
 
2-4, N (%)
 
TASH score, mean (SD)
 
 - 0-17, N (%) - 18-31, N (%) 
BATT score, mean (SD)
 
 - 0-7, N (%) - 8-12, N (%) 
Death due to bleeding, N (%)
 
Massive transfusion, N (%)
 
Early Death (<24h), N (%)
 
 - < 12h, N (%) - 12-24 h, N (%)

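### The SAP's bleeding-death proxy assumes that eligibility has already removed asphyxia and hanging, but the criteria remove choking or hanging only without other injury, so some of these deaths could be counted as bleeding deaths

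*SAP*

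**What the plan says.** The proxy is defined in the SAP's missing-data part, section 5.2.2 on early deaths as a stand-in for death due to bleeding. It applies when death due to bleeding is missing, and the SAP says it is not known whether the registry records cause of death. The proxy has two parts:

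- **0–12 hours after injury:** all deaths whatever the cause, less those with massive skull or brain destruction.
- **12–24 hours:** only deaths with evidence of bleeding, namely activation of a massive transfusion protocol, blood given within 6 hours, or one of a list of haemorrhage-related AIS diagnoses.

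The first part has a parenthesis explaining why no other cause is carved out: "asphyxia, drowning and hanging are already excluded from the STR".

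SAP section 4.2 says that registry patients "have been recorded according to these inclusion criteria of the STR", so the lists that follow are offered as the registry's own. Section 4.2.2 excludes "Drowning patients" without condition, but for the other group it excludes only a "Choking or Hanging patient without any other injury". The Protocol synopsis has the same condition: "Choking or hanging patient without any other injury". The injury threshold for entry is "ISS (Injury Severity Score) ≥ 16 and/or AIS head (Abbreviated Injured scale) ≥ 3".

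**The concern.** The parenthesis is the only reason the SAP gives for having no rule on asphyxia and hanging. By naming these causes beside skull and brain destruction, the SAP shows that it does not want them counted as bleeding deaths. If eligibility does not remove them, the definition followed as written does what its authors meant to avoid. This is an incorrect premise inside an outcome definition.

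The proxy can stand in for a named secondary outcome, and SAP section 5.2.1.1 applies the full set of performance analyses to secondary outcomes. Section 5.2.4 says that BATT cannot be calibrated against massive transfusion, and assigns its calibration to death due to bleeding or early death. A non-bleeding death counted as an event raises the observed count and lowers the predicted-to-observed ratio. If the question is left open, someone will have to decide after seeing the deaths whether a hanging with a head injury counts. Posting the SAP before the data arrive is meant to prevent that kind of choice.

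**Working it through.** The plan gives no figure on this point, so the check is mainly a comparison of texts.

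**Step 1. Test the parenthesis cause by cause against SAP section 4.2.2 and the Protocol synopsis.**

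| Cause | Parenthesis in the proxy | Eligibility criteria | Supported? |
|---|---|---|---|
| Drowning | already removed | excluded outright | yes |
| Hanging | already removed | excluded only if there is no other injury | in part |
| Choking | not named, unless meant by asphyxia | excluded only if there is no other injury | in part |
| Asphyxia in general | already removed | not named | no |

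No other place in either document closes the gap.

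**Step 2. Ask whether such a patient can be eligible.** Take an adult found hanging who also has other injuries, with ISS of at least 16 and AIS head of at least 3, and who is treated in the trauma room. Both limbs of the injury threshold are met, so the loosely worded exclusion in section 4.2.2 (ISS below 16 and/or AIS head below 3) does not apply on any reading. The hanging exclusion does not apply because there is another injury. The patient is eligible.

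**Step 3. Apply the proxy.** Suppose the patient dies at 4 hours without massive skull or brain destruction. The 0–12 hour part asks for no evidence of bleeding, so the death counts. The same death at 14 hours would need evidence of bleeding.

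**Step 4. List the conditions that must hold together.**

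1. Death due to bleeding is missing and the proxy is used.
2. The patient was choked, hanged or asphyxiated, and also has another injury that meets the entry threshold.
3. Death occurs within 12 hours.
4. There is no massive skull or brain destruction.

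**Step 5. Size.** The documents give no number of such deaths, so the effect cannot be calculated. For illustration, let *f* be the share of all proxy events (both time windows) that are non-bleeding deaths of this kind. Observed events are then the true number × 1/(1 − *f*), and the predicted-to-observed ratio is multiplied by (1 − *f*). The values of *f* are assumptions:

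| *f* | Observed events, 1/(1 − *f*) − 1 | Multiplier on predicted/observed |
|---|---|---|
| 0% | 0% | 1.00 |
| 1% | 1/0.99 − 1 = +1.0% | 0.99 |
| 5% | 1/0.95 − 1 = +5.3% | 0.95 |
| 10% | 1/0.90 − 1 = +11.1% | 0.90 |

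Nothing in the documents favours one row over another.

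**The case against.** The strongest reply is that this is a wording mismatch with little behind it. All four conditions must hold together, the primary outcome is not involved, and the affected patients may be very few. The proxy is crude by design: it already counts other non-bleeding deaths in the first 12 hours, including head-injury deaths short of massive destruction. This stands as a limit on size. It does not remove the contradiction, because the SAP singles out these causes as ones that should not be counted.

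Several stronger readings are tempting, and the documents do not support them:

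- **That avalanche or crush asphyxia is a known contributor.** Table 2 does list "Gunshot - Stabbing - Explosion - Avalanche" among circumstances, but as potential baseline categories and not as causes of asphyxia. The word asphyxia in the parenthesis may simply paraphrase choking.
- **That hanged patients who enter will usually carry another coded injury.** This depends on how AIS codes hanging and anoxia, which the documents do not describe.
- **That any patient with AIS head 3 is eligible.** With ISS below 16 this is unclear, because of the and/or in the exclusion list. The example above avoids this by meeting both thresholds.
- **That these deaths flatter BATT.** The text available lists the items of TASH and ABC but not of BATT, so the direction of any effect on its discrimination cannot be shown.
- **That the proxy is necessarily the BATT calibration outcome.** Section 5.2.4 also allows early death, a separate outcome that does not depend on this carve-out.

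It is also fair to object that removing every asphyxia death, whatever else is coded, could discard patients who did bleed to death. That stands, and it shapes the fix.

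**Conclusion.** The point holds in limited form. The statement that asphyxia and hanging are already excluded is right for drowning, partly right for hanging, and unsupported for asphyxia in general. Followed as written, the proxy would count as a bleeding death an eligible choking, hanging or asphyxia patient with another qualifying injury who dies within 12 hours without massive skull or brain destruction.

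A reader might infer that bleeding deaths will certainly be inflated by a material amount. The documents do not support that: the number is not given, may be small or zero, and matters only if cause of death is not recorded and the proxy is used. What is exposed is one secondary outcome, for all scores analysed against it, and any BATT calibration that uses the proxy. The massive transfusion analyses and all-cause early death are untouched.

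The conclusion assumes that the section 4.2 lists state the registry's criteria, as the SAP says they do. If the registry in fact applies a wider exclusion, the lists need correcting instead. The correction is still worth making, because the premise can be checked from the text, it sits inside an outcome definition, and it is cheap to put right before the data are seen.

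**What to change.** Reconcile SAP section 4.2.2 with the proxy definition in section 5.2.2:

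1. Correct the parenthesis to say that registry eligibility removes only drowning, and choking or hanging without other injury.
2. Exclude from the 0–12 hour part any death identifiable from type of accident or AIS codes as hanging, choking or other asphyxia, unless it meets the evidence-of-bleeding criteria that the SAP already lists for 12–24 hour deaths. This keeps patients who were asphyxiated and also bled.
3. Report how many deaths the rule reclassifies, and run a sensitivity analysis with them counted.

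The cost is about one sentence in the SAP plus one sensitivity run. Type of accident, AIS codes and timed red cell units are all requested in Table 1. There are two downsides. There may be a few fewer proxy events. The rule also depends on how the registry codes type of accident: the circumstances in Table 2 include no category for hanging or choking, so some cases may sit under other or unknown. The SAP should say how deaths that cannot be classified are handled.
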